## 7.0 RECRUITMENT PLAN

Potential research subjects will be identified by a member of the patient's treatment team, the protocol investigator, or research team at Memorial Sloan Kettering Cancer Center (MSK) and the participating institutions. If the investigator is a member of the treatment team, s/he will screen their patient's medical records for suitable research study participants and discuss the study and their potential for enrolling in the research study. Potential subjects contacted by their treating physician will be referred to the investigator/research staff of the study.

During the initial conversation between the investigator/research staff and the patient, the patient may be asked to provide certain health information that is necessary for the recruitment and enrollment process. The investigator/research staff may also review portions of their medical records in order to further assess eligibility. They will use the information provided by the patient and/or medical record to confirm that the patient is eligible and to contact the patient regarding study enrollment. If the patient turns out to be ineligible for the research study, the research staff will destroy all information collected on the patient during the initial conversation and medical records review, except for any information that must be maintained for screening log purposes.

In most cases, the initial contact with the prospective subject will be conducted either by the treatment team, investigator, or the research staff working in consultation with the treatment team. The recruitment process outlined presents no more than minimal risk to the privacy of the patients who are screened and minimal PHI will be maintained as part of a screening log. For these reasons, we seek a (partial) limited waiver of authorization for the purposes of (1) reviewing medical records to identify potential research subjects and obtain information relevant to the enrollment process; (2) conversing with patients regarding possible enrollment; (3) handling of PHI contained within those records and provided by the potential subjects; and (4) maintaining information in a screening log of patients approached.

Potential study participants who meet our basic inclusion/exclusion criteria will be approached by their physician to volunteer for this study. If the patient indicates a willingness to participate, a consenting professional (board-certified oncologist) will explain the study in detail. All study recruitment will be done by MSK, and the participating institutions. The total accrual goal is 63 evaluable patients. A total of 43 patients will be enrolled at MSKCC and a total of 20 patients will be enrolled at the participating external institutions (10 patients at Stanford University and 10 patients at Dana Farber Cancer Institute). We anticipate consenting approximately 4 patients per month.

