## 1.0 PROTOCOL SUMMARY AND/OR SCHEMA

This is a multi-center, open-label, phase 2 trial testing the efficacy and safety of 2 interventions that target rash during PI3K inhibitor therapy in postmenopausal women and men with histologically-confirmed, hormone receptor (HR)-positive, HER2-negative, PIK3CA mutant metastatic breast cancer (MBC). A total of 63 patients will be enrolled into one arm: benralizumab 30mg in combination with standard of care (SOC) endocrine therapy (fulvestrant or AIs or aromatase inhibitors (AIs)) and PI3K inhibition (alpelisib). A total of 43 patients will be enrolled at MSKCC and a total of 20 patients will be enrolled at the participating external institutions (10 patients at Stanford University and 10 patients at Dana Farber Cancer Institute). The primary endpoint is the proportion of patients with grade  $\leq 1$  rash rate at 4 weeks.

**Patient Population:** The primary study population will be postmenopausal women and men with histologically-confirmed, HR-positive, HER2-negative, *PIK3CA* mutant MBC who have received no more than 2 lines of endocrine-based therapy in the metastatic setting.

**Design:** A multi-center, open-label, phase 2 trial testing the efficacy and safety of one interventions (one anti IL-5 receptor antibody and one antihistamine) that target the maculopapular rash during PI3K inhibitor therapy in patients with HR-positive, HER2-negative, *PIK3CA* mutant MBC receiving first or second line therapy. Study participants (n=112) will enrolled to one arm: benralizumab (anti-IL5ra) in combination with SOC endocrine therapy (fulvestrant or AIs) and PI3K inhibition (alpelisib). The primary endpoint is the grade  $\leq 1$  rash rate at 4 weeks. The study size is determined to compare the grade  $\leq 1$  rash rate at four weeks with historical controls. It has been reported that approximately 34% of patients receiving alpelisib will develop  $\geq$  grade 2 rash within the first 30 days. The corollary is that 66% of historical controls will have grade  $\leq 1$  rash within the first 30 days. An increase in rash control to approximately 88% is deemed to be clinically meaningful with the investigational agent under investigation (IL5r antibody). A sample size of 57 patients per group will achieve an 80% power to detect an odds ratio of 4.0 with respect to the primary endpoint. The proportion in the experimental group is assumed to be 0.66 under the null

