hypothesis and 0.88 under the alternative hypothesis. The proportion is 0.66. If it is assumed that 10% of patients will withdraw consent or be lost to follow up, then 63 patients will need to be enrolled into this trial.

**Treatment Plan:** All participants will receive SOC endocrine therapy (fulvestrant or AIs) and PI3K inhibition (alpelisib). Participants will receive benralizumab 30mg subcutaneously on day -1. All participants will be monitored at regular visits for the duration of the trial. After 4 weeks, patients will be followed for safety at 90 days and disease progression for 1 year.

**Estimated Time to Completion:** 1 years.

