## 4.0 OVERVIEW OF STUDY DESIGN/INTERVENTION

### 4.1 Design

This is a prospective, MSK investigator-initiated, multi-center, open-label, phase 2 trial testing the efficacy and safety of one interventions that targets interleukin 5 receptors during PI3K inhibitor therapy in patients with HR-positive, HER2-negative, *PIK3CA* mutant MBC receiving first or second line therapy. Study participants (n=63) will be treated with benralizumab in combination with SOC endocrine therapy (fulvestrant or AIs) and PI3K inhibition (alpelisib). Crossover will not be allowed. The primary endpoint is the grade ≤1 rash rate at 4 weeks.

Postmenopausal women and men with histologically-confirmed, HR-positive, HER2-negative, *PIK3CA* mutant MBC who have received no more than 1 line of endocrine-based therapy in the metastatic setting will be eligible. Study recruitment will be done by MSK and the participating institutions. Patients will be screened by members of the institution's breast oncology service. Those deemed eligible will complete baseline skin exam, skin tape stripping, blood work and urinalysis (See section 9.0).

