## 14.0 BIOSTATISTICS

### Sample Size

This will be a single arm trial. The target sample size is intended to test the hypothesis that benralizumab reduces the frequency of grade  $\geq$  grade 2 rash at 4 weeks relative to the historical controls in patients receiving alpelisib. The primary endpoint in the current study will be the proportion of patients to achieve a rash grade of 1 or less. It has been reported that approximately 34% of patients receiving alpelisib will develop  $\geq$  grade 2 rash within the first 30 days. An increase in rash control to approximately 88% is deemed to be clinically meaningful with the investigational agent. Sample sizes of 57 patients achieves an 80% power to detect a difference based on a two sample proportions test. Due to potential attrition during the course of the study, the sample size will be increased by 10%. The resultant sample size will be 63 patients.

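### The accrual goal of 63 evaluable in Section 7.0 and the n=112 in Section 1.0 conflict with the derived target of 63 enrolled

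*Combined protocol and SAP*

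**What the plan says.** Most of the protocol gives 63 as the number enrolled, treated or finally required:

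- Section 1.0, opening paragraph: "A total of 63 patients will be enrolled into one arm".
- Section 1.0, end of the Design text, after a 10% allowance for withdrawal and loss to follow-up: "then 63 patients will need to be enrolled into this trial".
- Section 4.1: "Study participants (n=63) will be treated with benralizumab".
- Section 14.0, Sample Size, where 57 is increased by 10%: "The resultant sample size will be 63 patients".

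Two statements differ:

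- Section 7.0: "The total accrual goal is 63 evaluable patients". The next sentence there gives the quotas: "A total of 43 patients will be enrolled at MSKCC and a total of 20 patients will be enrolled at the participating external institutions". The 20 external patients are split 10 and 10 between two institutions.
- Section 1.0, Design paragraph: "Study participants (n=112) will enrolled to one arm".

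Evaluable and enrolled are separate counts in this protocol. Section 12.0 ties evaluability for the primary endpoint to obtaining the 4-week endpoint. Section 14.0 restricts all efficacy analyses to a modified ITT population of patients with a 4-week efficacy assessment.

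**The concern.** Section 7.0 attaches the enrolment number to the evaluable count. A goal of 63 evaluable and quotas of 63 enrolled can both be met only if nobody is lost, yet Sections 1.0 and 14.0 plan for 10% loss. Section 1.0 also gives 63 and 112 for the same single arm.

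What is at stake is the point at which enrolment closes, and whether a patient without a 4-week assessment is replaced. A centre with a quota of 10 cannot settle the second question from Section 7.0. In an open-label, single-arm trial whose data go for statistical analysis quarterly (Section 14.0), the closing number should be fixed in advance and stated in only one way.

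**Working it through.** **Inputs.** Null and alternative rates of grade 1 or lower rash: 0.66 and 0.88 (Section 1.0). Power 80%, n = 57, two-sample proportions test (Section 14.0; Section 1.0 gives 57 per group). Attrition 10% (Sections 1.0 and 14.0). Quotas 43, 10 and 10 (Sections 1.0 and 7.0). Alpha and sidedness are not stated; I assume 0.05 two-sided because that reproduces 57. One-sided 0.05 would give 45.

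**Step 1: reproduce the 57.** Pooled two-sample formula without continuity correction:

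n = [1.960 × √(2 × 0.77 × 0.23) + 0.842 × √(0.66 × 0.34 + 0.88 × 0.12)]² / 0.22²

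= [1.960 × 0.5951 + 0.842 × 0.5745]² / 0.0484 = 1.650² / 0.0484 = 56.2, rounded up to 57.

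Power at 57 is 80.5%, so the plan's figure is confirmed under the assumed alpha. The variants do not match: 66 with continuity correction, 54 with unpooled variance.

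**Step 2: reproduce the 63.** 57 × 1.10 = 62.7, rounded up to 63. This is the method in Section 14.0. Dividing by retention instead gives 57/0.90 = 63.3, or 64, a difference of one patient. The quotas agree: 43 + 10 + 10 = 63.

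**Step 3: follow each statement through 10% loss.** Power uses the same two-sample formula.

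| Statement followed | Enrolled | Evaluable | Power |
|---|---|---|---|
| 63 enrolled (1.0, 4.1, 14.0, quotas) | 63 | 63 × 0.90 = 56.7 | 79.8% at 56; 80.5% at 57 |
| 63 evaluable (7.0) | 63/0.90 = 70 | 63 | 84.4% |
| n=112 (1.0, Design) | 112 | 112 × 0.90 = 100.8 | 96.4% at 100 |

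The second row exceeds the quotas by 70 − 63 = 7, and the third by 112 − 63 = 49. At the roughly 4 consents a month expected in Section 7.0, and if every consent becomes an enrolment, the three readings take 63/4 = 15.75, 70/4 = 17.5 and 112/4 = 28 months.

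**Step 4: look for a source for 112.** It is neither 57 nor 63 under any 10% inflation. It equals 2 × 56, but no sentence derives it.

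**Step 5: the odds ratio (side point).** Section 1.0 states power "to detect an odds ratio of 4.0". The stated rates give (0.88/0.12)/(0.66/0.34) = 3.78. An odds ratio of exactly 4.0 gives odds of 4 × 0.66/0.34 = 7.76, hence a rate of 7.76/8.76 = 0.886, for which the same formula needs 53 rather than 57. The 57 therefore rests on 0.66 v 0.88.

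**The case against.** The best case against the point is that the intended number is clear. Sections 1.0, 4.1 and 14.0 all give 63, two of them with its derivation, and the quotas add to 63. The Design text that contains n=112 itself ends with 63 to be enrolled. The n=112 also sits beside wording about an antihistamine and a sample size per group, which suggests a leftover from a two-arm design. That explanation is inference; the protocol does not say so. On this view the two statements are stray text, not rival plans.

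Most of this stands, and it limits the consequence. It rules out three stronger readings that a reader might infer:

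- *That the evaluable number behind the power claim is undefined.* It is 57, given in Sections 1.0 and 14.0, and it reproduces. Being 56.7 rather than 57 after loss is a shortfall of 0.3 of a patient.
- *That a site is likely to enrol towards 112, or well past its share.* Explicit quotas totalling 63 precede the n=112 sentence in Section 1.0 and follow the evaluable goal in Section 7.0.
- *That the odds ratio of 4.0 is a sample-size error.* The target is described as approximately 88%, so 3.78 against 4.0 is close to rounding and has no bearing on when enrolment stops.

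The objection does not remove the contradiction. Both statements are current text, and the one in Section 7.0 is in the section that governs recruitment. Sites should not have to infer an accrual ceiling by weighing one section against another.

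**Conclusion.** The point holds as an inconsistency in a number the trial relies on. Section 7.0 (63 evaluable) and the Design paragraph of Section 1.0 (n=112) cannot stand beside the derived target of 63 enrolled once the planned 10% loss is applied. Read literally, enrolment closes at 63, 70 or 112.

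The consequence is confined to that closing number. On the plan's own two-sample formula, power is 79.8% to 80.5% if 63 are enrolled and higher on the other readings, so none takes it materially below 80%. These power figures assume a two-sided alpha of 0.05 and exactly 10% attrition. The contradiction itself does not depend on the alpha assumption. Whether a two-sample formula suits a one-arm comparison with a historical rate is a separate question, not judged here.

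**What to change.** - Section 7.0: replace the evaluable goal with *63 enrolled, to give about 57 evaluable (modified ITT)*. This agrees with the quotas and links evaluable to the population defined in Section 14.0.
- Section 1.0, Design paragraph: replace n=112 with n=63.
- Sections 1.0, 4.1, 7.0 and 14.0: use the same enrolled figure throughout, with the same evaluable figure wherever one is given.
- Optional: in Section 1.0, give the effect only as 0.66 v 0.88, or state the odds ratio as 3.78.

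The cost is an amendment of wording. No more patients are needed, and the quotas and the power calculation stay as they are.

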### **7.1 Research Participant Registration**

Confirm eligibility as defined in the section entitled Inclusion/Exclusion Criteria. Obtain informed consent, by following procedures defined in section entitled Informed Consent Procedures. During the registration process registering individuals will be required to complete a protocol specific Eligibility Checklist. The individual signing the Eligibility Checklist is confirming whether the participant is eligible to enroll in the study. Study staff are responsible for ensuring that all institutional requirements necessary to enroll a participant to the study have been completed. See related Clinical Research Policy and Procedure #401 (Protocol Participant Registration).

### **7.2 Randomization**

No randomization will occur in this study. After eligibility is established and immediately after consent is obtained, patients will be registered in the Clinical Trials Management System (CTMS).

## **8.0 INFORMED CONSENT PROCEDURES**

This consent form meets the requirements of the Code of Federal Regulations and the Institutional Review Board/Privacy Board of this Center. The consent form will include the following:

1. The nature and objectives, potential risks and benefits of the intended study.
2. The length of study and the likely follow-up required.
3. Alternatives to the proposed study. (This will include available standard and investigational therapies. In addition, patients will be offered an option of supportive care for therapeutic studies.)
4. The name of the investigator(s) responsible for the protocol.
5. The right of the participant to accept or refuse study interventions/interactions and to withdraw from participation at any time.
6. How the participants' data will be protected, who will have access to their PHI, and what data will be disclosed for research purposes

Memorial Sloan Kettering Cancer Center  
[name]  
[name]

Prior to inclusion in the study and before protocol-specified procedures are carried out, the consenting professionals will explain the details of the protocol as outlined in the consent and research authorization to the participants/LARs. The participant/LAR will also be informed that they are free to withdraw from the study at any time. The consent discussion may occur in person or remotely via teleconference, telephone, or videoconference.

All participants/LARs must sign an IRB/PB-approved consent form/research authorization indicating their consent to participate. Each participant/LAR and consenting professional will sign and date the consent form. The participant/LAR must receive a copy of the signed informed consent form.

## 9.0 PRE-TREATMENT/INTERVENTION

Patients who consent to the study will require the following tests within 14 days prior to treatment start:

1. History (including menstrual history) and dermatologic exam
2. Consent to Protocol
3. Review of concomitant medications
4. Vital signs (blood pressure, heart rate, temperature), height, weight
5. ECOG performance status
6. Toxicity (symptom) Assessment QOL will be assessed using the Functional Assessment of Cancer Therapy – Breast (FACT-B) scale developed for the assessment of patient symptoms and QOL in breast cancer patients and the PRO-CTAE. Allergy questionnaire will also be administered to identify history of atopic disease.
7. Baseline Data Form
8. Standardized total body photography
9. Skin tape stripping in 2 locations
10. Evidence of disease evaluation as per SOC, such as:
  1. Diagnostic CT chest/abdomen/pelvis scan OR MRI chest/abdomen/pelvis scan

## 10.0 TREATMENT/INTERVENTION PLAN

Patients will receive fulvestrant or AIs 500 mg IM on days 1, 15, 29 and once monthly thereafter. Alpelisib 300mg by mouth once daily will be initiated with the first fulvestrant or AIs dose (day 1). Patients will continue alpelisib and endocrine therapy until disease progression or unacceptable toxicity as determined by their treating clinician.

Patients will receive benralizumab on day -1 to -7 of alpelisib initiation. Skin tape strips and research blood will be collected prior to alpelisib initiation.

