### 4.2 Intervention

Eligible patients will undergo screening and baseline procedures per the pretreatment study schedule (Section 8.0). Study inclusion and exclusion criteria will be applied per section 6.0. Patients will undergo SOC histologic assessment and genomic analysis, and research blood testing. Once eligibility is confirmed, patients will receive benralizumab.

Patients will receive fulvestrant or AIs and PI3K inhibition (alpelisib) per SOC (fulvestrant on days 1, 15, 29 and monthly thereafter; AIs on a daily continuous basis). Participants will receive one injection of benralizumab 30mg subcutaneously on day -1.

Adherence, tolerance, and adverse effects (AEs) of the therapeutic agents will be evaluated at weeks 2 and 4. Research staff and investigators will review adherence and tolerance medications, AEs or intolerance, and collect skin tape strips, urinalyses, and research bloods or biopsies per Section 11.0.

Safety will be evaluated in this study through the monitoring of all serious and non-serious AEs, graded according to National Cancer Institute Common Terminology Criteria for Adverse Events, version 5.0 (NCI CTCAE v5.0).

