## **6.0 CRITERIA FOR PARTICIPANT ELIGIBILITY**

### **6.1 Participant Inclusion Criteria**

Memorial Sloan Kettering Cancer Center  
[name]  
[name]

1. Histologically confirmed metastatic HR-positive, HER2-negative breast cancer. HR positive is defined by ER status >10% immunohistochemical (IHC) staining of any intensity.
2. Must be scheduled to receive SOC endocrine therapy (alpelisib plus fulvestrant or AIs)
3. Presence of one or more activating *PIK3CA* mutations in tumor tissue.
4. Measurable disease per RECIST v1.1 OR at least one predominantly lytic bone lesion must be present.
5. Written informed consent provided
6. Female or male  $\geq 18$  years of age
7. Eastern Cooperative Oncology Group performance status of 0 or 1.
8. Life expectancy  $\geq 6$  months.
9. Adequate organ and marrow function as defined below:
  - Hemoglobin  $\geq 8.0$  g/dL (without blood transfusion within 7 days of laboratory test used to determine eligibility)
  - Absolute neutrophil count  $\geq 1.0 \times 10^9/L$  (without granulocyte colony stimulating factor support within 2 weeks of laboratory test used to determine eligibility)
  - Platelet count  $\geq 50 \times 10^9/L$  (without transfusion within 2 weeks of laboratory test used to determine eligibility)
  - Total bilirubin (TB)  $\leq 1.0 \times$  institutional upper limit of normal (ULN; Patients with known Gilbert's disease who have TB  $\leq 3 \times$  ULN may be enrolled)
  - Aspartate transaminase/alanine transaminase  $\leq 2.5 \times$  ULN with normal alkaline phosphatase ( $\leq 5 \times$  ULN for patients with liver metastases) OR  $\leq 1.5 \times$  ULN in conjunction with alkaline phosphatase  $>2.5 \times$  ULN
  - Creatinine  $\leq 1.5$  mg/dL.
10. Able to swallow oral medication.
11. Willing to be treated in the study arm and able to comply with the protocol for the duration of the study including undergoing treatment and scheduled visits and examinations
12. Women must be of postmenopausal status. Postmenopausal status is defined by any one of the following criteria:
  - Prior bilateral oophorectomy
  - Age  $\geq 60$  years
  - Age  $<60$  years and amenorrheic for at least 12 months (spontaneous cessation of menses for 12 consecutive months or more in the absence of chemotherapy, tamoxifen, toremifene, or ovarian suppression) and follicle-stimulating hormone and estradiol levels in the postmenopausal range without an alternative cause.

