### Fulvestrant or AIs

There is no dose modification for fulvestrant or AIs

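### Section 10.0 puts aromatase inhibitors on the fulvestrant injection calendar, while Section 4.2 has them taken daily; the two must be reconciled

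*Combined protocol and SAP*

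**What the plan says.** Section 10.0, the treatment plan, reads: "Patients will receive fulvestrant or AIs 500 mg IM on days 1, 15, 29 and once monthly thereafter". It continues: "Alpelisib 300mg by mouth once daily will be initiated with the first fulvestrant or AIs dose (day 1").

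Section 4.2 says endocrine therapy and alpelisib are given according to standard of care, and separates the two classes: "fulvestrant on days 1, 15, 29 and monthly thereafter; AIs on a daily continuous basis". It gives no dose or route for either.

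AIs are a permitted partner for alpelisib. Inclusion criterion 2 in Section 6.1 reads "Must be scheduled to receive SOC endocrine therapy (alpelisib plus fulvestrant or AIs"), and the summary in Section 1.0 also names both classes.

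**The concern.** Section 10.0 is where a site looks for what to give and when. Read as written, its dose, route and calendar govern AIs as well as fulvestrant. Section 4.2 gives AIs a different schedule, and an AI cannot be both given on days 1, 15 and 29 and taken every day.

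A site that gives AIs daily departs from Section 10.0. A site that follows Section 10.0 departs from Section 4.2. This matters for compliance because Section 16.3 has every participating site work from one protocol document and provides for protocol compliance audits. Section 7.0 plans 43 patients at the lead site and 10 at each of two external sites, so the text will be read by teams who did not draft it.

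**Working it through.** There is no planned figure to reproduce, because the point uses no alpha, power, effect size or event count. The check is a comparison of the places that mention endocrine therapy.

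**The two schedules**

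| | Section 10.0 | Section 4.2 |
|---|---|---|
| Fulvestrant, calendar | days 1, 15, 29, then monthly | days 1, 15, 29, then monthly |
| AI, calendar | days 1, 15, 29, then monthly | daily, continuous |
| Fulvestrant, dose and route | 500 mg IM | not stated |
| AI, dose and route | 500 mg IM, by wording | not stated |

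The fulvestrant calendars agree. The AI calendars do not. Over days 1 to 28, Section 10.0 gives an AI patient 2 dosing days (1 and 15), and Section 4.2 gives 28. On dose and route there is no second figure to compare, so the direct conflict is confined to the schedule.

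**Does any other text settle it?**

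- Section 5.0 describes alpelisib and benralizumab but no endocrine agent.
- The endocrine paragraph under dose modifications in Section 10.0 says only: "There is no dose modification for fulvestrant or AIs".
- Table 9 in Section 11.0 has no endocrine therapy row.

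Section 10.0 is therefore the only place that states an endocrine dose or route.

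**Does the conflict reach any analysis?**

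- Day 1: Table 9 labels it as the start of alpelisib.
- Time to rash (Section 13.2): counted in days from day 1, so from the start of alpelisib.
- 4-week relative dose intensity (Section 13.2): cumulative dose over the first 4 weeks after starting alpelisib, divided by the standard dose. Neither its origin nor its dose terms involve endocrine therapy.
- Primary endpoint and sample size (Sections 13.1 and 14.0): grade 1 or lower rash at 4 weeks, 57 patients raised to 63. The endocrine dose or schedule does not enter.

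**How many participants?** The documents do not say what share will take an AI. The range is 0 to 63.

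**The case against.** The strongest reply is that this is an editing slip that nobody would act on. The words for AIs seem to have been inserted after fulvestrant throughout the text. The summary has "endocrine therapy (fulvestrant or AIs or aromatase inhibitors (AIs")), and Section 3.3 is garbled in a similar way. Endocrine therapy is background standard of care, patients must already be scheduled for it, and Section 5.0 lists only benralizumab and alpelisib as supplied drugs. No individual AI is named, so Section 10.0 is hardly a usable AI order, and Section 4.2 states the AI schedule plainly.

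Much of this stands. An insertion error is the likely cause, though that is an inference, and the standard-of-care wording makes actual harm unlikely. It lowers the weight of the point but does not remove the contradiction, because the faulty sentence is in the treatment plan itself.

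Three stronger readings are tempting and are not supported:

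- A reader might infer that the sections contradict each other on dose and route. They do not, since Section 4.2 gives neither.
- A reader might infer that the day 1 phrase in Section 10.0 leaves the origin of time to rash or of relative dose intensity open for a patient already on a daily AI. Table 9 and Section 13.2 fix both at the start of alpelisib. The phrase leaves unclear only how AI dosing lines up with that start, and the documents describe no such patient, although no eligibility criterion excludes one.
- A reader might infer a demonstrated patient-safety problem. The documents offer no evidence of one.

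**Conclusion.** The point holds, as a minor one. Sections 10.0 and 4.2 give incompatible AI schedules, and Section 10.0 also attaches a dose and route to AIs by its wording alone. The conclusion rests on reading the Section 10.0 sentence as written and on finding no text elsewhere that resolves it. The consequence is an unclear dosing instruction and uncertain compliance for AI-treated participants, whose number is not given. No statistical quantity in the plan changes.

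**What to change.** The sponsor should reconcile Section 10.0 with Section 4.2 so that fulvestrant and AIs each have their own stated instruction, in the same terms in both places. The Section 10.0 phrase that ties the start of alpelisib to the first endocrine dose should be aligned with Table 9, where Day 1 is already the start of alpelisib. What the instructions should be is for the sponsor to decide; no dose or schedule is proposed here. The cost is a wording amendment, with no change to the sample size, endpoints or analyses.
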